17.7.4 Adverse events

An overview of all AEs, including SAEs, intensity, and deaths will be presented by study part and IP. The incidence of AEs and SAEs will be summarized by SOC and PT for each study part and IP.

All AE data will be listed by subject number and include the verbatim term entered by the Investigator.

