8.1.2 Part 2: single IP use in a 5-way cross-over

At Visit 4, the subjects will return to the study site for the first IP use visit of Part 2.

Subjects shall abstain from tobacco/nicotine products as well as smoking (cigarettes or ecigarettes) for 12 hours prior to each IP use visit (Visits 4 to 8). All IP use sessions will be performed during the morning hours (08:00 to 12:00) to facilitate abstinence.

The IPs will be administered as single pouches/portions in a pre-determined randomized order. Randomization will take place before the first IP use of Part 2.

Subjects will keep the pouch/portion between their lip and gum for 30 minutes and will be instructed not to eat, drink, chew gum, or brush their teeth for 30 minutes before, during, and 30 minutes after the IP use.

After 30 minutes, each used pouch/portion will be collected and frozen (-20°C) pending analysis of residual nicotine content. Unused pouches/portions from the same batch will serve as references and will be stored at -20°C pending analyses.

Blood samples for the assessment of nicotine plasma levels and PK parameters will be collected at pre-defined time points from pre-use to 6 hours after each IP use. The PD effects of the IPs will be determined using pulse rate measurements and subjective parameters (using VAS questions) at the same pre-defined time points as well as a multiple-choice question (MCQ) 30 minutes after IP use.

CONFIDENTIAL 30(76)

AEs will be collected through subject interviews and will also include any AEs reported spontaneously by the subjects, starting from the initiation of IP use (Visit 4), and continuing until the last IP use visit (Visit 8).

Visits 5 to 8 will follow the same schedule as Visit 4. Each visit will be scheduled on separate days, preferably with at least 24 hours between visits. However, it is acceptable to have visits on consecutive days, as long as all 5 visits are not scheduled consecutively.

At the end of *Visit 8*, the subject will receive one can of each of the three moist NP products with varying strengths (6 mg, 11 mg, and 16.6 mg) used in Part 2. Importantly, the subjects will be blinded to the nicotine strength of these three products. The subject will test these at home over 2-3 days to ensure they find a suitable replacement for their own brand snus product to be used in Part 3.

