8.1.3 Part 3: Ad libitum use of nicotine pouch product

At Visit 9 (first day of Part 3), the subjects will return to the study site and then the chosen NP product (6 mg/unit, 11 mg/unit or 16.6 mg/unit) will be documented. Based on the subject's reported consumption, they will be provided with the NP product to be exclusively used ad libitum for 14 days (allowed time window: +3 days). During this visit, subjects will undergo interviews regarding any experienced AEs. Subjects will be reminded on how to document their consumption using the eDiary and how to collect used pouches. The subjects will also be provided with collection containers for storing the used pouches and a cooling bag for transportation of the used pouches to the study site.

From the day after *Visit 9*, subjects will completely switch from their own brand snus product to the chosen moist NP product for 14 days, using it *ad libitum*. Subjects will document their consumption once per day via an eDiary throughout the 14-day study period (recording the number of pouches used per day, the estimated usage time per pouch, and whether they opened a new can). Additionally, subjects will collect 4 used pouches on two separate days during the first week (Samples A) and on two separate days during the second week (Samples B), storing them in freezer (\leq -18°C). In total, 8 pouches will be collected per week.

At Visit 10 (14 days after Visit 9) the subjects will return to the study site in the morning. They will bring the collected frozen pouches for extraction analysis. During this visit, subjects will undergo interviews regarding any experienced AEs, the NP product used, and their compliance with the eDiary will be assessed. Additionally, a 24-hour urine collection (allowed time window: ±15 minutes) will begin in the morning. Subject will remain on-site until the following morning, using the selected NP product ad libitum. The urine will be continuously collected during this period for the analysis of BoE.

The subject may leave the study site after completion of the 24-hour urine collection and final assessment of AEs and concomitant medications. This is the end of the subject's study participation.

CONFIDENTIAL 31(76)

Table 8.1-1 Overall schedule of events

Events	CSP section	Visit 1 Screening	Visit 2	Visit 3	Visit 4	Visit 5	Visit 6	Visit 7	Visit 8	Test period	Visit 9	Visit 10
			Pa	rt 1			Part 2				Pa	rt 3
Informed consent	11.3.1	X										
Demographics	11.3.2	X										

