11.2 Electronic patient reported outcome

To fill in the eDiary, the subjects themselves will record data using an electronic patient reported outcome (ePRO) system (ViedocMeTM) linked to the eCRF. The ePRO system includes password protection and internal quality checks.

The subjects will receive eDiary training and instructions at Visit 2 (reminder if needed on Visit 9). The subjects will be instructed to record eDiary data once daily (for the previous calendar day) during the 14-days *ad libitum* use periods of Part 1 and 3. The following data will be collected:

- the number of pouches/portions used
- estimated average use time for each pouch/portion (in minutes)
- if a new box of pouches/loose snus was opened that day (yes/no)

Text reminders to fill in the eDiary will be sent through ViedocMeTM. The site personnel will perform an eDiary compliance check when the subject returns to the site on Visit 3 and 10. All ePRO data will be stored together with the eCRF data.

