11.5.4.3 Time period and frequency for collecting adverse events

All AEs (including SAEs) will be collected from the start of first IP use in Part 2 until the last visit (Visit 10).

Any AE with start date on the day of each IP use must be recorded with start time.

On the last IP use visit (Visit 10), information on new AEs or SAEs, if any, and stop dates for ongoing events must be recorded as applicable.

Investigators will not be obliged to actively seek AEs or SAEs after conclusion of the study participation. However, if the Investigator learns of any SAE, including a death, at any time after a subject has been discharged from the study, and they consider the event to be reasonably related to the study intervention or study participation, the Investigator must promptly notify the Sponsor.

CONFIDENTIAL 49(76)

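### Adverse events in the 2-3 day home test between Visits 8 and 9 are collected but cannot be reliably assigned to a nicotine strength, because use by can and day is not recorded

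*Protocol*

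**What the plan says.** Section 17.7.4 sets the AE tables: "The incidence of AEs and SAEs will be summarized by SOC and PT for each study part and IP".

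Section 8.1.2 sets a hand-out at Visit 8, once the last supervised use is over: "the subject will receive one can of each of the three moist NP products with varying strengths (6 mg, 11 mg, and 16.6 mg"). It adds: "The subject will test these at home over 2-3 days". On blinding it says: "Importantly, the subjects will be blinded to the nicotine strength of these three products". Section 8.1.3 then dates the next part: "At Visit 9 (first day of Part 3), the subjects will return to the study site". Table 8.1-1 gives the test period a column of its own between Visit 8 and Visit 9.

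On AE collection, Section 11.5.4.3 says: "All AEs (including SAEs) will be collected from the start of first IP use in Part 2 until the last visit (Visit 10"). Section 8.1.3 adds an AE interview at Visit 9. The Part 2 text in Section 8.1.2 and in the synopsis methodology, however, ends collection at Visit 8, while the synopsis safety paragraph ends it at Visit 10.

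On recording of use, Section 11.2 says: "The subjects will be instructed to record eDiary data once daily (for the previous calendar day) during the 14-days", meaning the ad libitum periods of Parts 1 and 3. Section 10.4 describes a site log of dates and quantities of product received and used by each subject.

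**The concern.** Secondary objective 4 is the safety and tolerability of each pouch strength and of the comparators. A table by study part and product needs two things for every event: a part, and the product in use at onset. For the home test the first is unclear and the second is not collected.

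The home test is also the only period of unsupervised use in which subjects hold all three strengths before choosing one. Part 2 covers one 30-minute use per visit after at least 12 hours of abstinence, and Section 6.3.1 itself expects daily nicotine exposure to be lower on those visits. The possibility of higher exposure than usual is placed by Sections 6.3.1 and 6.3.3 in ad libitum use. If test-period events cannot be tied to a strength, the only by-strength evidence on repeated use is from Part 3, where each strength is used by those who picked it after trying the alternatives.

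**Working it through.** **1. Which part?** The home test is described in the Part 2 section (8.1.2), has a separate column in Table 8.1-1, and precedes Visit 9, where Part 3 starts. Filing it under Part 2 is possible, but would mix unsupervised home use of up to three products with supervised single uses.

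**2. Which product?** The possible sources are:
- eDiary (11.2): runs only in the two 14-day periods.
- Accountability log (10.4): dates and quantities per subject. Return of unused product is marked in Table 8.1-1 only at Visit 10. At best this gives a total per can, not which can was used on the day an event began.
- AE interview at Visit 9 (8.1.3): captures the event, but the subject does not know the strengths and has no dated record of cans.
- Own brand snus: the complete switch starts the day after Visit 9 (8.1.3), and the nicotine restrictions in 9.6.1 are written for Parts 1, 2 and 3. Own brand use in the test period is therefore not excluded.

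The rule in 17.1.1 for a missing AE start time is anchored to product intake, and no home intake times are recorded. Nor is any minimum use per can set, so the number exposed to each strength at home is not known either.

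**3. What Part 2 supplies.** Section 17.2 plans 45 evaluable subjects, and 45 / (1 − 0.15) = 52.9, rounded up to 53 randomized, as stated. Every sequence in 9.9 contains all three strengths, so Part 2 gives 45 to 53 single uses per strength. For an AE with an assumed 5% incidence, the chance of at least one case is 1 − 0.95^n:
- n = 45: 90.1%
- n = 53: 93.4%

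**4. What Part 3 supplies.** The number choosing each strength is unknown. With the same formula and assumed numbers of users:
- 5 users: 22.6%
- 10 users: 40.1%
- 15 users: 53.7%
- 18 users: 60.3%
- 30 users: 78.5%

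Incidence over 14 days and incidence after one use are different quantities, so these figures only size the two sources.

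**5. Share of unsupervised pouch days.** The test lasts 2-3 days and Part 3 lasts 14 days with a window of +3:
- smallest share: 2 / (2 + 17) = 10.5%
- largest share: 3 / (3 + 14) = 17.6%

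**6. Illustration of self-selection, Part 3 table only.** All of the following are assumptions. Of 53 subjects, 20% would have an AE on a given strength (10.6) and 80% would not (42.4). The tendency repeats fully within subject. One third of tolerant subjects choose that strength: 42.4 / 3 = 14.13. Intolerant subjects choose it at the same rate reduced by an avoidance fraction a: (10.6 / 3) × (1 − a).
- a = 0: 3.53 / (3.53 + 14.13) = 20%
- a = 0.50: 1.77 / 15.90 = 11%
- a = 0.75: 0.88 / 15.02 = 6%
- a = 0.90: 0.35 / 14.49 = 2%

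**The case against.** The strongest reply is that by-strength tolerability already has a sound source. Part 2 randomizes every subject to a sequence with all three strengths and both comparators, each subject is their own control, and AEs are tabulated by product. That stands. A reader might infer that strength-specific tolerability as a whole rests on self-selected Part 3 users and is biased, or that a poorly tolerated strength will look safe. The documents do not support either inference.

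A reader might also infer that a test-period AE would be credited to the last product used at Visit 8. No such rule is stated.

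Self-selection in Part 3 is declared: that part is non-randomized and studies the choice of strength. Its AE tables are descriptive, with no between-strength test. This also stands, and limits the remedy for Part 3 to a label.

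It can be said that the placing of such events belongs in the SAP. That is right for the tabulation rule, but not for the missing data: no SAP can recover use by can and day. The investigator's causality assessment and the Visit 9 interview may settle individual cases, so attribution is unreliable rather than impossible.

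Finally, diary data would not resolve every event. Three cans tried in two days force at least one day with more than one can. That is true, and is why an unattributable category is needed.

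**Conclusion.** The point holds in a limited form. AEs with onset in the home test are within the collection window of Section 11.5.4.3, but cannot be reliably placed by strength in the tables of Section 17.7.4. By-strength tolerability under repeated ad libitum use then comes only from Part 3 subjects who chose their strength. The randomized comparison of single uses in Part 2 is unaffected.

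The gap covers 2-3 days, about 11% to 18% of unsupervised pouch days. The direction and size of any selection effect in Part 3 cannot be computed from the documents. The 11%, 6% and 2% figures rest entirely on assumed AE rate, repetition, choice and avoidance, concern only the descriptive Part 3 table, and show no bias when there is no avoidance.

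The Visit 8 end of AE collection may be meant only for Part 2. Read literally, it leaves out the test period and conflicts with the Visit 10 end stated elsewhere, so the passages need reconciling.

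**What to change.** - **Section 11.2 and Table 8.1-1:** extend the existing eDiary to the test period. Record for each day the number of pouches used from each coded can, with the strength not shown, and any own brand use. The site can link code to strength, since the chosen strength is documented at Visit 9.
- **Section 17.7.4:** report the test period as its own period, separate from supervised Part 2 uses. Attribute each AE to the can used that day, or to a multiple/unattributable category where more than one product was used or the record is missing. Give the number of subjects who used each can as the denominator.
- **Section 17.7.4:** label Part 3 AE rates by strength as applying to self-selected users.
- **Synopsis and Section 8.1.2 against the synopsis safety paragraph and Section 11.5.4.3:** reconcile the Visit 8 and Visit 10 ends of AE collection so that the test period is clearly covered.

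The cost is two to three more diary days on a system the subjects already use, one more column in the AE tables, and some wording. Some days will still be unattributable. Product use, blinding of subjects and the primary analysis do not change.

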17.8 Analysis of exploratory objectives

17.8.1 Exploratory subjective parameter (Part 2 only)

The subjective parameter "product-liking" vs. the subjects' usual snus/nicotine product of choice, measured through MCQ, will be summarized for each IP using descriptive statistics in a frequency table.

Additionally, the subgroup "loose snus users" will be analyzed and presented separately.

17.8.2 Extraction normalized AUC_{0-inf} and C_{max} (Part 2 only)

Nicotine extraction normalized PK parameters $AUC_{0\text{-inf}}$ and C_{max} (the PK parameter with and without baseline-adjustment, divided by the extracted amount) will be determined for the following products: NP 6 mg, NP 11 mg, NP 16.6 mg, as well as for the comparators: own brand snus pouch/loose snus and Swedish snus pouch 18 mg. The analysis will compare the differences in $AUC_{0\text{-inf}}$, C_{max} , and the extracted amount and fraction of nicotine between the NP 6 mg, NP 11 mg, and NP 16.6 mg products, as well as for the comparators (own brand pouch/loose snus and Swedish snus pouch 18 mg). This analysis will use the same model described in Section 17.6.1.

Additionally, extraction normalized AUC_{0-inf} and C_{max} data will be presented for each IP using summary statistics.

Additionally, the subgroup "loose snus users" will be analyzed and presented separately.

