At Visit 3 (14 days [allowed time window: +3days] after Visit 2), the subjects will return to the study site in the morning. They will bring the collected frozen pouches/portions for extraction analysis. During this visit, subjects will undergo interviews regarding their health status and medications used, the specific Swedish snus product they used (including its strength and flavor), and their compliance with the eDiary will be assessed. Additionally, a 24-hour urine collection (allowed time window: ±15 minutes) will begin in the morning. Subject will remain on-site until the following morning, using the snus product ad libitum. The urine will be continuously collected during this period for the analysis of biomarkers of exposure (BoE).

Part 2: Single IP use in a 5-way cross-over

At Visit 4, the subjects will return to the study site for the first IP use visit of Part 2.

Subjects shall abstain from tobacco/nicotine products as well as smoking (cigarettes or e-cigarettes) for 12 hours prior to each IP use visit (Visits 4 to 8). All IP use sessions will be performed during the morning hours (08:00 to 12:00) to facilitate abstinence.

The IPs will be administered as single pouches/portions in a pre-determined randomized order. Randomization will take place before the first IP use of Part 2.

Subjects will keep the pouch/portion between their lip and gum for 30 minutes and will be instructed not to eat, drink, chew gum, or brush their teeth for 30 minutes before, during, and 30 minutes after the IP use.

After 30 minutes, each used pouch/portion will be collected and frozen (-20°C) pending analysis of residual nicotine content. Unused pouches/portions from the same batch will serve as references and will be stored at -20°C pending analyses.

CONFIDENTIAL 6(76)

Blood samples for the assessment of nicotine plasma levels and PK parameters will be collected at pre-defined time points from pre-use to 6 hours after each IP use. The PD effects of the IPs will be determined using pulse rate measurements and subjective parameters (using visual analogue scale [VAS] questions) at the same pre-defined time points as well as a MCO 30 minutes after IP use.

AEs will be collected through subject interviews and will also include any AEs reported spontaneously by the subjects, starting from the initiation of IP use (Visit 4), and continuing until the last IP use visit (Visit 8).

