Visits 5 to 8 will follow the same schedule as Visit 4. Each visit will be scheduled on separate days, preferably with at least 24 hours between visits. However, it is acceptable to have visits on consecutive days, as long as all 5 visits are not scheduled consecutively.

At the end of *Visit 8*, the subject will receive one can of each of the three moist NP products with varying strengths (6 mg, 11 mg, and 16.6 mg) used in Part 2. Importantly, the subjects will be blinded to the nicotine strength of these three products. The subject will test these at home over 2-3 days to ensure they find a suitable replacement for their own brand snus product to be used in Part 3.

Part 3: Ad libitum use of nicotine pouch product

At Visit 9 (first day of Part 3), the subjects will return to the study site and then the chosen NP product (6 mg/unit, 11 mg/unit or 16.6 mg/unit) will be documented. Based on the subject's reported consumption, they will be provided with the NP product to be exclusively used ad libitum for 14 days (allowed time window: +3 days). During this visit, subjects will undergo interviews regarding any experienced AEs. Subjects will be reminded on how to document their consumption using the eDiary and how to collect used pouches. The subjects will also be provided with collection containers for storing the used pouches and a cooling bag for transportation of the used pouches to the study site.

From the day after *Visit 9*, subjects will completely switch from their own brand snus product to the chosen moist NP product for 14 days, using it *ad libitum*. Subjects will document their consumption once per day via an eDiary throughout the 14-day study period (recording the number of pouches used per day, the estimated usage time per pouch, and whether they opened a new can). Additionally, subjects will collect 4 used pouches on two separate days during the first week (Samples A) and on two separate days during the second week (Samples B), storing them in freezer (\leq -18°C). In total, 8 pouches will be collected per week.

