Epidemiological data, based on the historical use of traditional Swedish snus in Sweden, shows a highly reduced risk profile for Swedish snus compared to cigarettes. Due to the product category's relative novelty, long-term epidemiological data on NPs is not yet at hand. Given the reduced levels of toxicants in NPs compared to traditional Swedish snus, the epidemiological data on snus can be extrapolated to assess the long-term health risks associated with NP use. The extrapolation is justified as long as the nicotine exposure from NPs does not exceed that from traditional Swedish snus. With a daily consumption of 32.1 g loose snus [2], an extraction of 24 % after one hour of use, and an average nicotine concentration of 0.8 - 1.0%, the daily exposure of nicotine is estimated to be between 62 - 77 mg. NPs, however, have different extraction rates. In this calculation, data from marketed NPs was used. An extraction rate of 39% after one hour of use was estimated, and the average consumption of pouches was found to be between 8.6 - 12.3 per day [3]. A hypothetical nicotine amount of 16.6 mg per pouch would then result in a nicotine exposure of 56 - 80 mg, which is similar to the epidemiologic data for loose snus.

Traditionally, Swedish snus pouch products have contained around 8-10 mg/g of nicotine [4], with the market offering various products with both lower and substantially higher nicotine levels (up to 45 mg/unit). Before the first pouched snus, SMOKELESS, weighed 1 gram, was introduced in 1973, there was only loose snus. More of the famous brands followed with portion-packed versions, including Tre Ankare in 1976, General® in 1985, and Göteborgs Rapé in 1997. Between 1986-2000, the use of loose snus went from being used by 95% to 58% of exclusive snus users.

While most NP products on the Swedish market contain between 1.5 mg and 17 mg of nicotine per pouch, there are concerns about products containing significantly higher amounts. In extreme cases, certain NPs can contain up to 150 mg of nicotine per pouch. This high amount poses serious health risks, especially for new users or those with low nicotine tolerance. Due to these risks and other factors (see below), nicotine limits for NPs have been under discussion. The Swedish Institute for Standards (SIS) set a 20 mg/unit limit in 2020

CONFIDENTIAL 21(76)

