7.3 Exploratory objectives and endpoints

The exploratory study objectives and endpoints are presented in Table 7.3-1.

Table 7.3-1 Exploratory objectives and endpoints

No.	Exploratory objectives	No.	Endpoints ¹	Assessments	Analysis
1.	To evaluate the impact on "product-liking" vs. the subjects' usual Swedish snus product of choice by administering single doses of the moist NP 6 mg, 11 mg, and 16.6 mg	1.	Difference in "product-liking" vs. the subjects' usual Swedish snus product of choice between the moist NP 6 mg, 11 mg, and 16.6 mg products and the comparator product, Swedish snus 18 mg, measured on a 3-point scale using	(Section 11.6.1.1)	See Section 17.8.1.

CONFIDENTIAL 27(76)

	products and the comparator product, Swedish snus 18 mg.		a multiple-choice question (MCQ) 30 minutes after IP use.			
2.	To compare the nicotine extraction normalized PK parameters AUC _{0-inf} and C _{max} between the moist NP 6 mg, 11 mg, and 16.6 mg products and the comparator products, Swedish snus 18 mg and own brand snus product.	2.	Difference in nicotine extraction normalized AUC _{0-inf} and C _{max} between the moist NP 6 mg, 11 mg, and 16.6 mg products and the comparator products, Swedish snus 18 mg and own brand snus product.	(Section 11.6.1.2)	See Section 17.8.2.	
3.	To analyze the pattern of use during each of the two 14-day ad libitum usage periods of either own brand snus product usage or complete substitution with a moist NP product.	3.	Difference in the pattern of use during each of the two 14-day ad libitum usage periods of either own brand snus product usage or complete substitution with a moist NP product.	(Section 11.6.1.3)	See Section 17.8.3.	
4.	To compare the PK profile between the selected strength NP product and the usual brand snus product.	4.	To compare nicotine exposure (in Part 2), as measured by baseline-adjusted AUC_{0-inf} and C_{max} , between the selected strength NP product (in Part 3) and the usual brand snus product (in Part 1).	(Section 11.4.1)	See Section 17.8.4.	

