17.7.2 Pharmacokinetics of nicotine in plasma (Part 2 only)

The following non-compartmental PK parameters will be determined for each IP: AUC_{0-inf} , AUC_{0-last} , $AUC_{0-l.5h}$, C_{max} , T_{max} , and $T_{1/2}$. Where possible, both baseline-adjusted and non-adjusted PK parameters will be calculated.

 C_{max} and T_{max} will be derived from the observed nicotine plasma concentration data. AUC_{0-1.5h}, AUC_{0-last}, and AUC_{0-inf} will be calculated using log-linear trapezoidal interpolation. Calculations will be based on the actual sampling times recorded during the study. Concentrations below the lower limit of quantification (LLOQ) occurring before C_{max} will be treated as zero. Concentrations below LLOQ occurring after C_{max} will be omitted from the analysis. All baseline-adjusted PK parameters will be corrected for nicotine plasma concentrations at baseline (pre-use).

AUC_{0-inf} will be calculated as described in Section 17.4 above.

The continuous secondary PK parameters (i.e., all of the above except T_{max}) will be analyzed for both non-baseline-adjusted, and baseline-adjusted concentrations using the same model as described in Section 17.6.1 to assess non-inferiority between each test product and each comparator product respectively.

In addition, descriptive statistics for secondary PK parameters and concentrations (baseline-adjusted and non-baseline-adjusted) will be presented. PK plasma concentration curves over time will be presented.

All data will be listed by subject number.

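### Extraction-normalized AUC0-inf and Cmax without baseline adjustment (Protocol 17.8.2) are inflated for products with a smaller extracted amount whenever pre-use nicotine is present

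*Protocol*

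**What the plan says.** Exploratory endpoint 2 (Table 7.3-1) is worded "To compare the nicotine extraction normalized PK parameters" AUC0-inf and Cmax between the three nicotine pouches and the two comparators. The table does not say whether the parameters are baseline-adjusted.

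Section 17.8.2 settles this by using both: "the PK parameter with and without baseline-adjustment, divided by the extracted amount". The parameters "will be determined for the following products: NP 6 mg, NP 11 mg, NP 16.6 mg", own brand snus and Swedish snus 18 mg. On the comparison it says "This analysis will use the same model described in Section 17.6.1", that is, the mixed model on the log scale that yields ratios of geometric means. Neither version is designated as the one on which conclusions rest.

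The extracted amount is defined in 17.7.1 as the content of an unused reference unit minus that of the used study unit. On baseline correction, 17.7.2 states "All baseline-adjusted PK parameters will be corrected for nicotine plasma concentrations at baseline (pre-use". On the run-up to each Part 2 session, the synopsis states "Subjects shall abstain from tobacco/nicotine products as well as smoking (cigarettes or e-cigarettes) for 12 hours prior to each IP use visit". On spacing it adds "However, it is acceptable to have visits on consecutive days, as long as all 5 visits are not scheduled consecutively".

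**The concern.** The natural purpose of an extraction-normalized parameter is to show how much nicotine reaches plasma per mg released from the product. That needs numerator and denominator to refer to the same nicotine. With baseline adjustment they do. Without it, the numerator also holds what remained from earlier use, and the denominator has no counterpart for it.

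Some residual nicotine is foreseen. Subjects use at least 5 units a day (9.4), abstain for 12 hours and may attend on consecutive days, and the protocol plans a correction for the pre-use level. In the randomized crossover the expected residual is the same whichever product is used. Divided by a smaller extracted amount, it adds more. The three pouches differ 16.6/6 = 2.77-fold in labelled content, so the artefact could look like less uptake per mg at higher strength. How nicotine content affects exposure is part of the study's overall aim (6.2).

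**Working it through.** The protocol states no figure for this endpoint, so there is none to reproduce. The sample size in 17.2 belongs to the primary endpoint and has no bearing here.

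**Inputs.** From the protocol: pouch contents of 6, 11 and 16.6 mg; snus content of 18 mg; the definition in 17.8.2; and, in 6.1, for pouches, "An extraction rate of 39% after one hour of use was estimated", with 24% after one hour for loose snus. Not in the protocol: any pre-use concentration or half-life. The residual is therefore an assumption, shown as a range.

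**Formula.** Let A be the AUC from the product, B the AUC from pre-use nicotine and E the extracted mg. The unadjusted normalized value is (A + B)/E = A/E + B/E. If uptake per mg is equal, A/E is the same for all products and only B/E differs. Taking logs does not remove this: log[(A + B)/E] = log(A/E) + log(1 + B/A), and the last term is larger where A is smaller.

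Write b for B as a share of the NP 16.6 mg product AUC, and assume equal extracted fractions. For a pouch of d mg, the ratio to NP 16.6 mg is

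r(d) = (1 + b × 16.6/d) / (1 + b).

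Example, b = 0.10 and d = 6: (1 + 0.10 × 2.767)/1.10 = 1.2767/1.10 = 1.161.

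| Residual b | NP 6 / NP 16.6 | NP 11 / NP 16.6 |
|---|---|---|
| 0 | 1.000 | 1.000 |
| 1% | 1.017 | 1.005 |
| 2% | 1.035 | 1.010 |
| 5% | 1.084 | 1.024 |
| 10% | 1.161 | 1.046 |
| 20% | 1.294 | 1.085 |

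The true ratio is 1.00 throughout.

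**Check on concentration curves, including Cmax.** A 30-minute constant input with first-order decay was evaluated at the protocol's sampling times, using a linear-up/log-down trapezoid and extrapolation to infinity. Assumed values: half-life 1.5 to 3 h, pre-use level 0.5 to 3 ng/mL, NP 16.6 mg Cmax 15 to 25 ng/mL. Over that range the unadjusted NP 6 / NP 16.6 ratio was 1.03 to 1.28 for AUC/E and 1.03 to 1.27 for Cmax/E. NP 11 / NP 16.6 for AUC/E was 1.01 to 1.08. With the decaying residual removed, the NP 6 / NP 16.6 AUC/E ratio was 1.000.

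**Contrasts with snus 18 mg.** The bias follows extracted mg, not the label. The 6.1 fractions are for one hour, whereas Part 2 use lasts 30 minutes, and the 24% is for loose snus, so applying it to the 18 mg pouch is a further assumption. Extracted amounts are then:

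- NP 6 mg: 6 × 0.39 = 2.34 mg
- NP 11 mg: 11 × 0.39 = 4.29 mg
- NP 16.6 mg: 16.6 × 0.39 = 6.47 mg
- Snus 18 mg: 18 × 0.24 = 4.32 mg

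With f(E) = 1 + b × 6.47/E, the ratios at b = 5% and 10% are:

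- NP 11 / snus 18: 1.000 and 1.001
- NP 6 / snus 18: 1.059 and 1.110
- Snus 18 / NP 16.6: 1.024 and 1.045

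No such figure can be given for own brand snus, because its content varies by subject.

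**The case against.** **The sound analysis is already planned.** The adjusted version is computed next to the unadjusted one, a gap between them would itself point to residual nicotine, and 17.1 has significant findings reviewed for medical relevance. This stands, and it confines the point to one half of one exploratory endpoint. It does not remove the point: where the two versions disagree, nothing says which governs.

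**The residual may be trivial.** Section 8.2 gives avoidance of carry-over as the reason for the abstinence. At a residual of 1% to 2% the worst pouch contrast is off by only 2% to 3.5%, and at zero there is no bias. The documents cannot settle the size.

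**The largest figures come from the most extreme contrast.** Table 7.3-1 sets pouches against comparators, and NP 6 mg against NP 16.6 mg enters only through the looser wording of 17.8.2. This also stands, and the snus 18 mg contrasts are smaller.

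**Two stronger readings are tempting.** A reader might infer that the 17.6.1 model would falsely reject a null of equal uptake per mg at some computable rate. The protocol states no such null and no two-sided test of ratio = 1 for this endpoint. The only hypothesis in 17.6.1 is the upper bound of 1.25. If that rule were carried over, the bias would make it harder to meet for a pouch that extracts less than its comparator. Any rejection rate would be illustrative only.

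A reader might also infer that the study will report less-than-proportional uptake at higher strength. The adjusted result would stand beside it, and the residual level is unknown, so the documents do not support that either.

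**Conclusion.** The concern holds as a minor point about the unadjusted half of exploratory endpoint 2. The mechanism and its direction are certain for any non-zero pre-use level, for both AUC0-inf and Cmax. The size is not fixed by the documents. Over assumed residuals of 1% to 20% of the NP 16.6 mg product AUC, the distortion is about 2% to 29% for NP 6 mg against NP 16.6 mg and 0.5% to 8.5% for NP 11 mg against NP 16.6 mg. It is close to nil for NP 11 mg against snus 18 mg on the section 6.1 fractions. These figures assume linear kinetics, equal true uptake per extracted mg and, among the pouches, equal extracted fractions.

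The adjusted half is free of the bias provided the correction removes the decaying residual. The primary endpoint and exploratory endpoint 4 use baseline-adjusted parameters without normalization and are untouched. Unadjusted AUC and Cmax keep a clear meaning as total exposure; they lose it only when divided by the extracted amount.

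**What to change.** In 17.8.2, base the model comparison on the baseline-adjusted extraction-normalized AUC0-inf and Cmax only, and say so in Table 7.3-1, no. 2. Either drop the unadjusted normalized version or keep it as descriptive output without inference. Keep unadjusted AUC and Cmax in un-normalized form, as 17.7.2 already plans. The cost is a change of wording in two places and fewer model outputs. Nothing changes in design, sampling or data collection.
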